6.2.1 Screening Evaluation

Consenting Procedure

The consent process will be conducted in a quiet, private room. During the consent process, potential participants will be informed about the study purpose and procedures and be given the opportunity to ask questions. They will be shown a video of the game to help them with the process. If they wish to continue, they will be asked to read and sign a single informed consent document. Next, a member of the research team will review the signed consent form and will ask the participant to explain the procedures in their own words to ensure that they comprehend the study procedures before proceeding to the initial assessment. Informed consent must be obtained before participants are screened. A copy of the signed and dated consent form will be given to participants, and the original document will be electronically stored on a secure server.

Pre-Screening

The purpose of pre-screening is to determine if the research candidates will qualify for the research. This web-based survey will take approximately 15-minutes to complete and includes the following forms:

- Numeric Pain Rating Scales 7-day & 24-hour
- Roland-Morris Disability Questionnaire
- Fear Question
- Medical History – Back Pain

Screening (Visit 0)

The purpose of the screening visit is to 1) describe the study protocol to candidates and begin the informed consent process, and 2) determine if study candidates will qualify for the study. The screening visit will take approximately two hours. During the screening visit the study coordinator will complete, in cooperation with the study candidate, the following:

- Numeric Pain Rating Scales 7-day & 24-hour
- Roland-Morris Disability Questionnaire
- Fear Question
- Medical History – Back Pain
- Medication Log
- Quebec Task Force Classification
- Informed Consent Form
- Inclusion/Exclusion Criteria Form
- Enrollment & Randomization Form
- Medical History
- Physical Exam

Re-screening participants may be considered and reviewed by the PIs on a case-by-case basis. Screening must occur within 30-days of prescreen completion. Visits 1 and 2 (Baseline and Intervention 1) may occur on the same day as screening and must occur within 7 days of screening. If these deadlines are not met the participants will be assigned a new PID, re-screened, and re-consented.

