4.3 Study Enrollment Procedures

When an individual expresses interest in the study, he or she will be directed to complete an online or phone Prescreen Assessment Questionnaire (CRFs VIGOR Pre-Screen) after providing assent to the prescreen. If a potential participant passes the initial eligibility screening, the study coordinator will contact the potential participants by e-mail and/or by phone to schedule a full screening assessment (Visit 0). At this time the study coordinator will verbally describe the study to the potential participant and answer any questions. The consent process will be conducted in a quiet, private room. During the consent process, potential participants will be informed about the study purpose and procedures and be given the opportunity to ask questions. They will be shown a video of the game to help them with the process. If they wish to continue, they will be asked to read and sign an informed consent document. Next, a member of the research team will review the signed consent form and will ask the participant to explain the procedures in their own words to ensure that they comprehend the study procedures before proceeding to the initial assessment.

Participants will then complete the screening visit surveys. Based on the responses to the questions, interested individuals who meet the inclusion/exclusion criteria will be identified and then undergo a physical exam by a licensed physical therapist or

physician. Participants who remain eligible following the physical exam will then be formally enrolled into the study. The study coordinator will then randomly assign them to their respective intervention group using a sex-stratified random allocation table.

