5. STUDY INTERVENTIONS

5.1 Interventions, Administration, and Duration

Participants will complete 18 intervention visits over 9 weeks with the number of sessions tapered across weeks (i.e., 3 sessions/week in weeks 1-3, 2 sessions/week in weeks 4-6, and 1 session/week in weeks 7-9).

Provision of Treatment Rationale: After completing all pre-treatment assessments, participants will be given a rationale for the intervention. This includes an educational component that will be used to correct biomedical misconceptions, explain how pain persists without underlying pathology, and describe the interaction among biological, psychological, and social factors in maintaining pain and disability. Further, as virtual dodgeball provides a unique platform to distract an individual from focusing on pain, the treatment rationale will be followed by 1) an initial exposure to the virtual dodgeball environment, 2) specific details on how the intervention is designed to promote increased spinal motion and decreased disability, and 3) an opportunity to play a practice level to review basic game constructs (e.g., scoring metrics, moving the avatar, sound and visual cues).

Virtual Environment: A head mounted display (e.g., HTC Vive) will be used to provide a virtual environment for both the weekly standardized reaching tasks and for gameplay. The head mounted display is used to present the virtual world with a screen refresh rate of 90 Hz. The environmental parameters are controlled by custom software developed in the Unity game engine to manipulate and control all presented graphics and audio. During the initial testing session and at each post treatment follow-up (1,6,12, 24, & 48 weeks), the 6-DOF kinematic data from the clusters of light reflective markers placed on the participant is streamed to the game environment at 100 Hz using Vicon Tracker software allows for near real time presentation of the participant's avatar. Motion Monitor software sets up bi-directional communication with the Unity game engine and records all kinematic data (e.g., joint excursions, joint moments) during the initial gaming session. This integration allows us to individualize the game experience to each participant. During the intervention visits, presentation of the participant's avatar is controlled through the 6-DOF position data from the head mounted display, hand controllers, and Vive trackers attached to the thorax and pelvis of the participant.

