6.1.1 Time between visits

[figure not shown]
- Prescreening to Screening is ≤ 30-days

- Screening to Baseline V1 is \leq 7-days
- Baseline V1 to Intervention V2 is \leq 7-days
- Intervention W1 V2 (T1), V3(T2), V4(T3) are 2-3-days apart (encompassing \leq 7-days)
- Intervention W2 V5 (T4), V6 (T5), V7 (T6) are 2-3-days apart (encompassing \leq 7-days)
- Intervention W3 V8 (T7), V9 (T8), V10 (T9) are 2-3-days apart (encompassing \leq 7-days)
- Intervention W4 V11 (T10), V12 (T11) are 2-6-days apart (encompassing \leq 7-days)
- Intervention W5 V13 (T12), V14 (T13) are 2-6-days apart (encompassing \leq 7-days)
- Intervention W6 V15 (T14), V16 (T15) are 2-6-days apart (encompassing \leq 7-days)
- Intervention W7 V17 (T16) is 6-10-days after previous Intervention V16
- Intervention W8 V18 (T17) is 6-10-days after previous Intervention V17
- Intervention W9 V19 (T18) is 6-10-days after previous Intervention V18
- Final Intervention V19 to First Post-Intervention Assessments V20 7-days +/- 3-days
- Final Intervention V19 to Post-Intervention Assessment V21 is 6-weeks +/- 1-week
- Final Intervention V19 to Post-Intervention Assessment V22 is 12-weeks +/- 1-week
- Final Intervention V19 to Post-Intervention Assessment V23 is 24-weeks +/- 1-week
- Final Intervention V19 to Post-Intervention Assessment V24 is 48-weeks +/- 1-week

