9.3 Definition of Populations

Intention to Treat Analysis (ITT): We will include all randomized study participants who have at least baseline endpoint assessments in our ITT analysis. The ITT analysis is our primary method for assessing outcomes, and how it is performed will be determined based on the pattern of missingness. If the missingness is deemed MCAR, the LOCF method will be used: simply the most recent valid observation will be "carried forward" to replace the subsequent missing observations. If the missingness is deemed MAR, missing observations will remain as missing, and

maximum likelihood estimation, the default estimation algorithm of LMER, will be used to estimate these observations. If the missingness is found to be MNAR, multiple-imputed data will be used to construct LMER models.

Per-Protocol Analysis (PPA): For the PPA we will exclude study participants who: 1) fail to attend 13 out of 18 treatment sessions; 2) develop an exclusionary medical condition while on study protocol, or 3) receive interventions outside of the Allowed (Section 5.3.1) during treatment. Finally, we will assess how comparable estimated parameters vary between ITT and PPA analyses.

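### The late-start rule in 6.2.1 gives a new PID to people who will normally already be randomised, does not protect their first allocation or baseline, and sets a limit that conflicts with 6.1.1

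*Combined protocol and SAP*

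**What the plan says.** On the deadline, 6.2.1 states: "Visits 1 and 2 (Baseline and Intervention 1) may occur on the same day as screening and must occur within 7 days of screening". The consequence follows at once: "If these deadlines are not met the participants will be assigned a new PID, re-screened, and re-consented". The same paragraph opens by leaving re-screening to case-by-case review by the investigators.

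Section 6.1.1 splits the interval in two. Screening to Visit 1 may take up to 7 days, and the entry beginning "Baseline V1 to Intervention V2 is" allows up to 7 days more. Section 6.2.2 has a third wording: at most 7 days from enrolment to either randomisation or the start of the intervention.

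On the timing of randomisation, 4.3 says: "Participants who remain eligible following the physical exam will then be formally enrolled into the study". Its next sentence has the study coordinator assign the arm from the allocation table. The schedule in 6.1 and the Visit 0 form list in 6.2.1 also put randomisation at Visit 0. The heading of 6.2.2 attaches it to Visit 1, with an and/or.

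On what happens at Visit 1, 5.1 says that once the baseline measures are done the participant receives a rationale with pain education, "an initial exposure to the virtual dodgeball environment", and a practice level. The Schedule of Interventions shows this introduction at baseline.

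On the analysis set, 9.3 says: "We will include all randomized study participants who have at least baseline endpoint assessments in our ITT analysis". Section 9.5.1 fixes the baseline of the co-primary outcomes at Visit 1.

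On late visits in general, 10.3.4 gives out-of-window visits as an example of a protocol violation and leaves continuation to the Steering Committee.

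**The concern.** Issuing a new PID and screening again is harmless before randomisation. The rule in 6.2.1 expressly covers the first intervention visit, which comes after randomisation in the ordinary course. For a randomised person, a new identity, a new consent and a repeat of the form that records randomisation look like a second entry into the trial. The documents do not say what becomes of the first entry.

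The integrity of the ITT set is at stake. One person should have one allocation and contribute one record. If both records stay, the mixed models, keyed to PID, would treat them as independent people. If the first is dropped, a randomised participant leaves the analysis after allocation. Re-screening also tests eligibility again, so a randomised person could be lost that way too.

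A repeated Visit 1 baseline would also follow the education, the VR introduction and the practice level. That matters most for expected pain, expected harm and lumbar flexion, the measures of Hypothesis 2.1.

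**Working it through.** **1. The windows.** Latest first intervention, counted from screening:

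- Section 6.2.1: day 7.
- Section 6.1.1: 7 (screening to Visit 1) + 7 (Visit 1 to Visit 2) = day 14.

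A Visit 2 on days 8 to 14 can satisfy 6.1.1 and still trigger the reset. The 30-day extension in 5.4 and 6.1.2 runs from Visit 2 to Visit 19, so it does not explain the gap. Under 6.2 the activity monitor is worn for a week after the baseline visit. If that week were completed before Visit 2, 6.2.1 would be met only with Visit 1 on the screening day (0 + 7 = 7). The plan does not require that order, and same-day visits are allowed.

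**2. Who is already randomised when the rule applies.**

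- Late from prescreen to screening (more than 30 days): before consent and randomisation, so harmless.
- Late for Visit 1: randomised if randomisation is at Visit 0; not yet if it is at Visit 1.
- Late for Visit 2 after Visit 1: normally randomised on either placement.

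**3. Effect on the ITT set of 9.3, if a second allocation is made.**

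- Randomised at Visit 0, Visit 1 missed: no Visit 1 baseline exists, so the first record falls outside the set as defined. The first allocation is lost.
- Randomised, Visit 1 completed, first record kept: two records for one person, possibly in different arms.
- Randomised, Visit 1 completed, first record dropped: the first allocation is lost although the person met the ITT definition.

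**4. The repeated baseline.** The Visit 1 introduction is not described as differing by arm, and the experimental gain is 1 both at baseline and in week 1. A shift in the second baseline would therefore be expected in both arms alike, unless resets themselves differ by arm. Sections 4.3, 6.2.2 and 6.2.3 together show that the unblinded coordinator both assigns arms and schedules visits, so such a difference cannot be excluded by design.

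**5. Scale, as illustration only.** The documents give neither a late-start rate nor an explicit allocation ratio. Suppose that a share r of 230 PIDs were re-entries, with 1:1 allocation and an independent second draw. Re-entries are k = 230r, expected changes of arm are k/2, and distinct people are 230 − k.

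| r | k (rounded) | k/2 | 230 − k |
|---|---|---|---|
| 2% | 4.6 → 5 | 2.5 | 225 |
| 5% | 11.5 → 12 | 6 | 218 |
| 10% | 23 | 11.5 | 207 |

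The rates are arbitrary. The table shows only how the problem scales.

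**The case against.** The best defence is that the protocol never says a late starter is randomised again. That is correct. A reader might infer that re-randomisation is ordered, but the text orders a new PID, re-screening and re-consent and is silent on allocation. What stands is that the repeated screening visit includes the randomisation form and that no sentence keeps the first allocation.

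Second, no section states 14 days. Any schedule that meets 6.2.1 also meets 6.1.1, so the former can be read as a stricter overall cap. That is fair, and 14 days should not be called authorised. But staff working from the visit list in 6.1.1 would find no cap, and exceeding it has a serious consequence.

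Third, the and/or heading and the 7-day sentence in 6.2.2 leave room for randomisation close to the first session, in which case the reset could reach only unrandomised people. This narrows the point, but 4.3, the schedule and the form list all favour Visit 0.

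Fourth, the case-by-case sentence in 6.2.1 and the deviation route in 10.3.4 give some discretion. Neither mentions allocation or the analysis set, and both sit uneasily with an automatic reset.

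Fifth, a reader might infer that Hypothesis 1 is distorted or that the second baseline follows allocated treatment. The documents do not support either. Hypothesis 1 concerns pain and disability, whereas the plausible shift is in the Hypothesis 2.1 measures. The exposure is introductory and not arm-specific. An allocated session would precede a second baseline only if Visit 2 took place on days 8 to 14 and the reset was applied afterwards.

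**Conclusion.** The concern holds in a limited form. Two things are firm: the reset as written reaches people who will normally already be randomised, with no rule for the first allocation or baseline; and 6.1.1 and 6.2.1 disagree for a first intervention on days 8 to 14. Double counting or loss of an allocation follows only if a second allocation is made, which is an inference, and double counting also needs a completed Visit 1. Bias between arms would further need resets that depend on arm. The documents show a route to that but no evidence that it happens.

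The number affected is unknown and may be small, since Visits 0, 1 and 2 may fall on one day. The point still deserves correction because it touches the definition of the primary analysis set.

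**What to change.** - Limit the new-PID and re-screening rule to candidates not yet randomised.
- State in 9.2 and 9.3 that each person is randomised once and analysed once, in the original arm, with the first Visit 1 baseline.
- Handle a late Visit 2 after randomisation as a visit-window deviation under 10.3.4.
- State one time point for randomisation in 4.3, 6.1, 6.2.1 and 6.2.2.
- Reconcile the windows in 6.1.1, 6.2.1 and 6.2.2.
- Link any PIDs that already belong to one person, while the code described in 11.3 still exists, and report the number of re-entries by arm.

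The cost is protocol wording and, if re-entries have occurred, a check of the PID list. A few participants will have a longer gap between baseline and first treatment, which the deviation log will show.

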6.2.2 Enrollment, Baseline, and/or Randomization (Visit 1)

Enrollment

A single informed consent form that describes both screening and study procedures will be used. The date of enrollment in The VIGOR Study will be defined as the date all of the screening criteria are met and the individual agrees to participate. The enrollment date will be recorded on a case report form along with the allowable window between screening and randomization.

- CRF: Randomization and Enrollment Form

Baseline Assessments

Participants enrolled in the study will complete the following baseline assessments at Visit 1:

- Numeric Pain Rating Scales 7-day & 24-hour
- Roland-Morris Disability Questionnaire
- Medication Log
- Adverse Events Log
- Numeric Pain Rating Scale – Right Now
- Standardized Reaching Paradigm (Pain & Harm Expectancy, Lumbar Spine Flexion)
- Tampa Scale for Kinesiophobia
- Center for Epidemiologic Studies – Depression
- Pain Catastrophizing Scale
- Pain Resilience Scale
- Pain Self Efficacy Questionnaire
- Brief Pain Inventory – Short Form
- PROMIS-Anxiety
- PROMIS-Depression
- PROMIS-Positive Affect
- PROMIS-Meaning and Purpose Scale
- Life Fulfillment Scale
- Profile of Mood States
- Real World Activity Monitoring
- Treatment Evaluation Inventory – Short Form

Randomization

The study coordinator will use a sex-stratified random allocation table, created by the study statistician, to assign participants to a treatment group. A maximum of 7-days will be permitted between enrollment and randomization or initiation of the study intervention.

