4.2 Exclusion Criteria

Candidates meeting any of the following exclusion criteria at baseline will be excluded from study participation:

- Has a personal history of the following neurological disorders: Alzheimer's, Amyotrophic Lateral Sclerosis, Multiple Sclerosis, Parkinson's, Neuropathy, Stroke, Seizures
- Has a personal history of the following cardiorespiratory disorders: Congestive heart failure, heart attack in past 2 years
- Has a personal history of the following musculoskeletal disorders: Rheumatoid Arthritis, muscular dystrophy, pathologic fractures of the spine, avascular necrosis or osteonecrosis, severe osteoarthritis
- History of spine surgery or a hip arthroplasty
- Has active cancer
- Has a chronic disease that may restrict movement or preclude safe participation
- Has used opioids within 30 days prior to study enrollment
- Reports being pregnant, lactating, or that they anticipate becoming pregnant within 2-months
- Reports pending litigation related to CLBP
- Has current drug or alcohol use or dependence that, in the opinion of the PIs, would interfere with adherence to study requirements
- Has significant visual impairment that would prevent virtual reality headset use
- Has significant motion sickness that would prevent virtual reality headset use

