6.2.3 Blinding

The principal investigators, the statistician, and members of the data collection team will remain blinded to intervention assignment throughout the duration of the study. They will be given the identifying codes only at the end of the study when it is necessary to interpret the results. The un-blinded study coordinator, who is responsible for scheduling testing and treatment sessions, will greet participants and

escort them to the testing lab; however, the study coordinator will not participate in the assessments of clinical outcomes or testing.

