Randomization & Stratification: The study statistician will use the R statistical language to block randomize treatments stratified by sex. Then the study coordinator will assign subjects to the treatment arms.

Masking or Blinding: The principal investigators, the statistician, and members of the data collection team will remain blinded to intervention assignment throughout the duration of the study. They will be given the identifying codes only at the end of the study when it is necessary to interpret the results. The un-blinded study coordinator, who is responsible for scheduling testing and treatment sessions, will serve to receive the study patients and escort them to the various testing and treatments sites to minimize the interaction between patients; however, the study coordinator will not participate in the assessments.

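### The un-blinded coordinator who screens candidates also assigns arms from a blocked table, and no step is described that hides the next assignment until eligibility is final

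*Combined protocol and SAP*

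**What the plan says.** **Assignment.** Section 6.2.2: "The study coordinator will use a sex-stratified random allocation table, created by the study statistician". Section 4.3 gives the order, with assignment following the physical exam and formal enrolment: "The study coordinator will then randomly assign them to their respective intervention group using a sex-stratified random allocation table". Section 9.2 adds that the statistician will "block randomize treatments stratified by sex" in R, after which the coordinator makes the assignments. Block size, allocation ratio and whether block size varies are not given.

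**Screening.** Under Section 4.3 the coordinator contacts candidates who pass the pre-screen, books Visit 0 and describes the study. Section 6.2.1: "During the screening visit the study coordinator will complete, in cooperation with the study candidate, the following". The list that follows includes the pain ratings, the RMDQ, the fear question, the Quebec classification, the inclusion/exclusion form and the enrolment and randomisation form. Section 11.2 has the coordinator, the principal investigators, or both, meet candidates for consent.

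**Blinding.** Section 6.2.3 describes "The un-blinded study coordinator, who is responsible for scheduling testing and treatment sessions" and keeps that person out of outcome assessment and testing. Sections 5.2 and 9.2 say essentially the same.

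**Discretion.** The exclusions in Section 4.2 include "Has a chronic disease that may restrict movement or preclude safe participation" and significant motion sickness. Section 6.2.2 allows up to 7 days between enrolment and randomisation or the start of the intervention.

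**The concern.** Randomisation protects against selection bias only if nobody who influences entry knows which arm comes next. Here the person who applies the allocation table is also the person who books candidates, fills in the eligibility paperwork and schedules the visits. If that person knows or can guess the next row, a borderline exclusion can be read one way or the other. Two eligible candidates of the same sex can also be taken in a chosen order. This need not be deliberate.

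The separation that the plan does provide acts after assignment. Keeping the coordinator away from outcome assessment protects measurement, not the make-up of the arms. Section 9.6 plans adjustment for age, BMI, radiating pain and variables that differ at baseline, but that cannot correct differences in prognosis that were not measured. The co-primary outcomes, pain and disability, are self-reported, and a coordinator who has met the candidate may well have formed a view of the likely course.

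**Working it through.** The plan gives no figure on this point, so there is nothing to reproduce. The check has four parts.

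**1. Who does what.**

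| Step | Person | Section |
|---|---|---|
| Contact after pre-screen, booking Visit 0 | Coordinator | 4.3 |
| Consent meeting | Coordinator and/or principal investigators | 11.2 |
| Screening and inclusion/exclusion forms | Coordinator, with the candidate | 6.2.1 |
| Physical exam | Licensed physical therapist or physician | 4.3 |
| Substance-use criterion | Principal investigators | 4.2 |
| Re-screening | Principal investigators | 6.2.1 |
| Assignment from the table | Coordinator | 4.3, 6.2.2, 9.2 |
| Scheduling of testing and treatment | Coordinator, un-blinded | 6.2.3 |

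The roster lists one study coordinator.

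**2. Any concealment step.** Sections 4.3, 5.2, 6.2.1 to 6.2.3, 9.2 and 11.2 mention no sealed assignments, no central or web release, and no lock on eligibility before an assignment is revealed. REDCap appears only for collecting and managing data (7, 7.1, 10.1). Enrolling first and assigning second, as in 4.3, helps only if the next row is unknown at enrolment.

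**3. Room to act on foreknowledge.** Some exclusions call for judgement (4.2). Screening may fall up to 30 days after the pre-screen, and baseline up to 7 days after screening (6.1.1). Up to 7 days may separate enrolment from randomisation (6.2.2). Missing the screening deadlines leads to a new participant number, re-screening and re-consent (6.2.1). Because rows are used in sequence within sex, the timing of assignment decides which row a person receives.

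**4a. Predictability if only past rows are known.** Assumptions: 1:1 allocation, permuted blocks of fixed size b, and b and past assignments known to the coordinator. The assignments known with certainty are the last unbroken run of one arm in each block. With h = b/2 per arm, the expected length of that run is 2h/(h + 1), so the share of participants whose arm is certain is 1/(h + 1) = 2/(b + 2).

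| b | Certain | Best guess correct |
|---|---|---|
| 4 | 2/6 = 33% | 71% |
| 6 | 2/8 = 25% | 68% |
| 8 | 2/10 = 20% | 67% |
| 10 | 2/12 = 17% | 65% |

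The best guess names the arm with more places left in the block. For b = 4 the chances of being right at positions 1 to 4 are 1/2, 2/3, 2/3 and 1, so the mean is 2.833/4 = 71%. Chance alone gives 50%.

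**4b. Size of bias, by assumption only.** Let s be the share of enrolments in each arm that are steered. Let k be the difference in mean prognosis, in outcome SDs, between the steered participants of the two arms. The arm difference shifts by s × k.

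| s (of 230) | k = 0.5 | k = 1 |
|---|---|---|
| 2% (about 5 people) | 0.01 SD | 0.02 SD |
| 10% (23 people) | 0.05 SD | 0.10 SD |

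Neither s nor k comes from the documents.

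**The case against.** The sponsor can fairly make four replies.

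- **Using a table is not the same as seeing all of it.** The wording also fits a process in which one row is shown at a time, and Section 12 refers to manuals of operations that are not part of these documents. This stands as far as it goes: visibility of future rows cannot be asserted. It does not fill the gap, because the protocol names the screener as the user of the table and sets no safeguard.
- **The coordinator is not the sole gatekeeper.** A reader might infer control of every entry step. The documents do not support that: a clinician's exam precedes enrolment, the principal investigators judge substance use and re-screening, and consent may be shared. Scheduling, the eligibility forms and the timing of assignment remain with the coordinator.
- **Many criteria leave little latitude.** Pain, RMDQ and Tampa scores have numerical cut-offs in 4.1, and pain and disability are the candidate's own reports. The enrolment date is also defined in 6.2.2 as the date when criteria are met and the person agrees. Both points are correct. What remains open is the judgement-based exclusions, for which no section says the coordinator decides alone, and the scheduling windows.
- **Block prediction needs knowledge that the coordinator may not have.** Nothing says that block size is fixed or known to the coordinator. This stands, so partial predictability under stated assumptions is all that can be claimed.

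**Conclusion.** The concern holds as a preventable weakness in the stated workflow. The un-blinded person who books candidates and completes their eligibility forms also assigns the arm from a blocked, sex-stratified table, and nothing described hides the next assignment until eligibility is final. This is more than thin reporting, because following the text as written leaves selection open to foreknowledge.

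Three stronger readings are tempting but unsupported. First, a reader might conclude that allocation is known to be unconcealed; the documents are silent on whether future rows can be seen. Second, a reader might suspect that entry was steered; nothing in the documents shows this. Third, a reader might express the bias as a share of the planned effect. No such share can be relied on. The numerator is assumed, and the denominator depends on the source: the stated f = 0.30 corresponds to d = 0.60 for two equal groups, whereas the Aim 1 inputs give 0.20/(0.75 × √0.6) = 0.344 on change scores.

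The shift of 0.01 to 0.10 SD therefore shows only what modest steering could do. The 33% to 17% certainty rests on 1:1 blocks of a known fixed size between 4 and 10. The point should be corrected, but it does not by itself invalidate the design.

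**What to change.** In Sections 4.3, 6.2.2 and 9.2, state that:

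- the coordinator does not receive the allocation list;
- the statistician's list is loaded into a system that releases one assignment at a time. REDCap can serve if its set-up here supports this; otherwise use sequentially numbered, sealed, opaque assignments;
- release happens only after the inclusion/exclusion form is complete and locked, with the time of release recorded;
- block sizes vary at random and are not disclosed to the coordinator. This weakens prediction from past assignments, though it cannot abolish it.

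The arms in the list can stay coded, so the statistician's blinding under 6.2.3 is unaffected. The text should also fix the visit at which release occurs, because the schedule in 6.1 marks enrolment and randomisation at Visit 0 while 6.2.2 places them under Visit 1. If a manual of operations already contains such a procedure, stating it in the protocol settles the point.

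The cost is minor set-up work and protocol wording. Sample size, outcomes and the planned models are unchanged.
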